4.4 Final Challenge Blinding

Although an open-label study, subjects, study coordinators and the primary investigator will remain blinded to subject's schedule of final DBPCFC challenge until 48th month DBPCFC is executed. Randomized week assignment for administration of the final challenge will be revealed only after the patient has completed the 48th month DBPCFC. Schedule randomization will be performed by representatives in [name] laboratory and all laboratory personnel will be unblinded to the randomization schedule throughout the study. All DBPCFCs are conducted in a double-blind manner.

4.5 Minimization of Missing Data due to Missed Visits during Tolerance Phase

To ensure minimization of missing data during the SU phase, the trial has been designed to encourage patient retention through multiple approaches, including provision of the possibility of "re-randomization" if more than one subject of the assigned week miss the visit they are scheduled at; or allowing a subject to take the final challenge on the study's next scheduled visit. The importance of minimizing the amount of missing data has been discussed with all study investigators, and their awareness of the importance of patient compliance and minimal dropout rates is factored into their recruiting plans. In addition, investigators are advised to contact the medical monitor for guidance on available management options when needed to prevent patients from withdrawing from the study.

5. ANALYSIS AND REPORTING

5.1 Interim Analysis

No interim analysis will be performed.

5.2 Final Analysis

All final, planned analyses will be performed after the last patient has completed the follow-up visit and end-of-study assessments and all relevant study data have been processed and integrated into the analysis database. Any post-hoc, exploratory analyses completed to support planned study analysis, which were not identified in this SAP, will be documented and reported in appendices to the CSR. Any results from these unplanned analyses (post-hoc) will also be clearly identified in the text of the CSR.

6. SAMPLE SIZE DETERMINATION

The sample size for this study has not been revised from the earlier estimated minimum required size of 50 subjects since the study is midway through with an existing enrollment of 51 subjects which we intuitively think is good enough with the new study design and analytical methods for the revised primary outcome of interest. However, to confirm our understanding, we plan on conducting simulations to study the power-sample size curve at 80% power based on study assumptions as discussed in the statistical methods section.

7. ANALYSIS POPULATIONS

The following analysis populations are planned for this study:

- **Safety Population (SAFETY):** all patients who receive at least 1 dose of investigational product. All safety analyses and demographic/baseline characterization will be performed using this population, analyzed as treated.
- **Intention-To-Treat Population (ITT):** all patients who are randomized for assessment of clinical desensitization and SU. This population is primary for efficacy and all efficacy analyses will be performed using this population.

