## STUDY DESIGN

This SLIT study is a prospective, randomized, open-label study based on previous experience at Duke University Medical Center using OIT and SLIT in food allergic subjects. The study will enroll 55 participants with peanut allergy with a goal of 50 children completing protocol interventions. Upon enrollment, all subjects will undergo an entry DBPCFC with 1000 mg of peanut protein to confirm the peanut allergy diagnosis and establish a baseline threshold level. Following a positive DBPCFC, each subject will begin the study drug with peanut SLIT at a starting dose of 1 pump of a 1/100 dilution of peanut concentrate (2500 mcg peanut protein). During the build-up phase which lasts approximately 20 weeks (Table 1), subjects will dose daily and increase the number of pumps every 1-2 weeks as per the dosing schedule. Subjects return to the research unit for observed dosing with each change in peanut SLIT dilution (1/100, 1/10, full concentration) and with every other dose increase on full concentration until the maintenance dose of 16 pumps of full concentration peanut SLIT (4000 mcg peanut protein) is achieved. Subjects will then continue daily administration of the maintenance dose and return every 6 months for follow-up.

After at least 48 months of peanut SLIT study drug, subjects will undergo a second DBPCFC to 5000 mg of peanut protein to assess desensitization.

- Subjects who are not desensitized are those who are not able to consume more than the MCRT without symptoms, which has been defined as 300 mg of peanut protein. Subjects who consume less than 300 mg of peanut protein without symptoms will stop peanut SLIT and conclude the study. These subjects will not undergo any additional study procedures including the remaining protocol DBPCFCs and will be recommended to resume a strict peanut avoidance diet.
- Subjects who are able to consume more than 300 mg of peanut protein will be randomized to an interval between 1 and 17 weeks during which all peanut including peanut SLIT study drug will be discontinued. This period of avoidance will be followed by a third DBPCFC to 5000 mg of peanut protein to evaluate for the loss of the desensitization effect. After this final DBPCFC, the study will be completed for these subjects. At the primary investigators clinical discretion, they will be recommended to transition to a daily peanut food equivalent to maintain the desensitized effect.

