4. OVERALL STUDY DESIGN AND PLAN

This is a Phase 2, open label 52-month study designed to evaluate the safety and efficacy of peanut SLIT in inducing clinical desensitization among peanut allergic children.

The study consists of a Screening visit, a Baseline Visit (sometimes combined with the Screening Visit), a build-up phase (approximately, 20 weeks), a Maintenance phase (42 months) and finally, a Sustained Unresponsiveness phase (17 weeks). The total duration of the study, including Screening and the follow-up period, is approximately 225 weeks. We note that all the 24 subjects that have passed the 48 month time point and have been waiting to be administered the 48th month DBPCFC are continuing to dose daily. Because, based on prior evidence, the benefit of continued dosing past 48 months is considered to be negligible on the overall treatment outcome, a slight extension of maintenance phase is considered negligible for such subject.

Following the qualifying entry 1000 mg peanut protein DBPCFC administered at the baseline, subjects will be administered diluted pumps of concentrated peanut protein extract (5000 mcg/ml) based on the build-up dosing scheme to reach an escalated dose of 4000 mcg. Visits for build-up doses will occur prior to changing peanut dilutions or every 4 weeks. Subjects completing the Duke IRB Pro0003579, UNC IRB 11-2301, CoFAR4 who do not pass the 164 week 10 gm DBPCFC may enroll in this study and resume an escalation schedule starting with the 2000 mcg dose in this SLIT (11-2308, TLC) protocol. This defines the build-up phase.

After completing the escalation schedule, subjects will continue to be administered 4000 mcg of peanut SLIT daily at home and will return to the clinical research unit for follow-up visits every 6 months or more frequently for new or significant symptoms. This defines the maintenance phase.

At the 48th month visit, all subjects undergo a 5000 mg peanut protein DBPCFC to verify desensitization, defined as a reaction threshold greater than MCRT (300 mg of peanut protein). At the same visit, subjects are randomized to one of the 17 weeks of SU phase for administration

of the final DBPCFC to assess SU. SU is claimed if the final DBPCFC reaction threshold is greater than or equal to the larger of MCRT and the 48th month DBPCFC sensitivity threshold. Subjects who fail the 48th month DBPCFC, hence not desensitized, will not be administered the final challenge.

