4.3 Method of Week Assignment for the Final Challenge and Randomization

The following criteria must be satisfied in order for the patient to continue to the SU phase of the study and be randomized:

1. The patient achieves MCRT at the 48th month DBPCFC to continue to the SU phase. This requires patient to be asymptomatic upon administration of 300 mg dose as assessed by Food Challenge Symptom Score sheet.
2. If subjects are found symptomatic and AEs that occur are considered to be intolerable at or below the MCRT, subjects will be refrained from taking the final challenge and will be considered to have lost their desensitization at week 0.
3. No subject will be administered a final challenge dose higher than the NOAEL attained at the 48th month DBPCFC.

Before the start of the SU phase of the study, a computer-generated block randomization schedule is prepared such that each subject has an equal probability of being randomized to one of the weekly challenges held in initial 6 weeks, between 7-12 weeks and between 13-17 weeks. Based on the randomization schedule, three qualified subjects are randomly assigned to one of the final DBPCFC administered each week during the study's 17-week SU phase.

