8. GENERAL ISSUES FOR STATISTICAL ANALYSIS

8.1 General Statistical Methodology

Descriptive summaries will be provided where appropriate for each of the primary and secondary variables.

Baseline characteristic and safety tables will be completed for the Safety Population unless otherwise specified. Baseline values are defined as the last non-missing measurement prior to the first dose of study drug. Change from baseline will be defined as the post-baseline visit value minus the baseline value.

Continuous, quantitative, variable summaries will include the number of patients (N) with non-missing values, mean and standard deviation, median, minimum, and maximum. Categorical, qualitative, variable summaries will include the frequency and percentage of patients who are in the particular category. In general the denominator for the percentage calculation will be based upon the total number of patients in the study population unless otherwise specified.

Efficacy tables will be presented for the ITT Population for each of the primary objectives. First, the number and proportion of subjects for each interval of NOAEL and LOAEL observed at the 48th month DBPCFC will be reported. This will be broken by baseline and other clinical characteristics. Non-parametric Kaplan-Meier estimates of NOAEL distribution with interval censoring will be used to report expected proportion of subjects within each interval of NOAEL and LOAEL, overall and by patient groups. Second, for each interval of NOAEL and LOAEL observed at the 48th month DBPCFC, Kaplan-Meier product limit estimates of the probabilities of loss of tolerance (as defined by the latter three efficacy outcomes in section 3.2.1 bullet 2) using interval censoring, will be plotted against time (17 weeks), overall and for various patient groups. The “expected” number of patients with loss of tolerance and the “P values” derived

from univariate log rank tests for interval censored data will be reported for each 48th month DBPCFC NOAEL.

Unless otherwise indicated, all statistical tests will be 2 sided and tested at a significance level of 0.05. Corresponding 95% confidence intervals will be presented for statistical tests.

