8.1.2 Event Censoring

- For efficacy endpoint in section 3.2.1 bullet 1 (population sensitization threshold), an individual's true threshold is
 - left censored if individual fails on the smallest dose administered
 - right censored if no adverse effect is observed on the largest dose administered
 - interval censored in all other cases.
- For the latter three time to loss of desensitization efficacy endpoints defined in section 3.2.1 bullet 2, censoring is defined as below:
 - Subjects with 48th month LOAEL < MCRT who are not administered the final DBPCFC have their time to loss of desensitization assumed to be zero.
 - Subjects with the final DBPCFC NOAEL equal to the highest administered dose level are assumed to have their LOAEL beyond the observed time.
 - For subjects who do not show up for the final DBPCFC until the 17th week of randomization will be removed from the analysis. A separate analysis will be conducted to predict drop-outs.

No censoring will occur on safety endpoints.

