10. EFFICACY ANALYSES

10.1 Primary Efficacy Analysis Approach

To begin with, our primary analysis will comprise of two parts.

First, an Interval-Censoring Survival Analysis (ICSA) approach will be used to analyze the 48th month DBPCFC threshold data (Collett, 1993, Chapter 9, Taylor et al - 2009). The methodology is appropriate when the exact dose that provokes a reaction in an individual is not known but it is known to fall into a particular interval. Using ICSA, if an individual had an objective reaction at the first dose in a challenge trial, then left-censoring occurred, and the NOAEL was set to zero with the LOAEL set as that first dose. If an individual did not experience an objective reaction after the largest challenge dose, then right-censoring occurred, and the NOAEL was set to that largest challenge dose (if a subjective response occurred at that largest dose, this was also considered as the objective NOAEL), while the LOAEL was set to infinity. In all other cases, interval-censoring occurs bounded by the NOAEL and LOAEL. Parametric (Log-normal, Weibull) and non-parametric dose-distribution model will be used to estimate the ED10 and the ED05, the doses predicted to provoke reactions in 10% and 5%, respectively, of the peanut-allergic population.

Second, for each dose interval bounded by the NOAEL and LOAEL of the 48th month DBPCFC, we will conduct survival analysis with case-1 censoring (Huang – Wellner lecture notes, Kosorok et al, 1998) to estimate time to loss of desensitization. We will assume exponential

distribution with log link for the decay of sensitivity threshold for those who take the final challenge. This assumption of exponential decay will be validated using semi/non-parametric analysis with an option for modeling with a more flexible **semi-parametric** distribution. The analyses will be performed with and without the effect of baseline and other clinical covariates. This analysis will provide an initial insight into effectiveness of peanut SLIT in longevity of induced clinical desensitization and SU.

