To illustrate, we introduce the following notation. Let X_d be the time to loss of desensitization with distribution F_d for a given NOAEL, d , administered at the 48th month DBPCFC ($d = 100, 200, 500, 800, 1300, 2100$ mg). Let T be an observation time (in weeks), $t = 0, 1 \dots 17$ with distribution G . Because the assignment time is randomized, the time of interest X_d and baseline covariates will be independent of T . We also assume that the clinically induced desensitization is monotonically decreasing such that the subject's NOAEL is either decreased or stays constant by observation time T . In other words, the true time to loss of desensitization from the 48th month DBPCFC, which is unknown, is either less or equal to the observation time. This could mathematically be represented as a problem of case-1 interval censoring wherein, we observe n i.i.d observations of $(T, I\{X_d \leq T\} | d) = (T, \Delta_d)$ for a given NOAEL, d . Further, we assume $X_d = 0$ for those subjects who do not meet MCRT ($d < MCRT$) at the 48th month DBPCFC. Let π define the probability that $X_d = 0$, and let the baseline and clinical covariates be represented by Z . Then, in order to derive the likelihood of F_d , we need to solve the following optimization problem to find the MLE:

$$\sup_{F \in \mathcal{F}} L_n(F)$$

, where \mathcal{F} is a class of distribution functions and

$$L_n(F) = \prod_{i=1..n} P(\beta, \gamma, Z_i, t)$$

$$\begin{aligned} P(\beta, \gamma, Z_i, t) &= \{P(X_{id} = 0) I(X_{id} = 0)\} * \{P(X_{id} > 0) I(X_{id} > 0)\} \\ &* \{P(X_{id} = t, \Delta = 0 | d, X_{id} > 0)\} * \{P(X_{id} = t, \Delta = 1 | d, X_{id} > 0)\} \\ &= \left[\frac{e^{\gamma' Z_i}}{1 + e^{\gamma' Z_i}} \right]^{y_i} * \left[\frac{1}{1 + e^{\gamma' Z_i}} \right]^{1-y_i} * [(1 - F_d(t))g(t)]^{1-\delta_i} * [F_d(t)g(t)]^{\delta_i} \\ &= \left[\frac{e^{\gamma' Z_i}}{1 + e^{\gamma' Z_i}} \right]^{y_i} * \left[\frac{1}{1 + e^{\gamma' Z_i}} \right]^{1-y_i} * (1 - F_d(t))^{1-\delta_i} * F_d(t)^{\delta_i} g(t) \end{aligned}$$

$$y_i = I(X_{id} = 0); \delta_i = I(\Delta_i = 1); F_d(t) = 1 - e^{-\lambda_i t}; \lambda_i(t, Z_i) = \lambda_0 e^{\beta' Z_i}$$

Maximizing the above likelihood will provide estimates of β & γ towards estimating distribution of time to loss of desensitization.

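### The SAP puts ED05/ED10 on randomised children only, yet children who react at or below 300 mg at month 48 are never randomised, which biases both doses upward if any child fails that gate

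*SAP*

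**What the plan says.** **Population.** SAP section 7 defines ITT as "all patients who are randomized for assessment of clinical desensitization and SU. This population is primary for efficacy and all efficacy analyses will be performed" on that set. SAP 8.1 applies this to the threshold results as well: "Efficacy tables will be presented for the ITT Population for each of the primary objectives", beginning with the month-48 NOAEL/LOAEL intervals. SAP 10.2 and Protocol 8.1.2 also confine the secondary efficacy analyses to ITT.

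**Who is randomised.** SAP 4.3 opens its list of conditions with "The following criteria must be satisfied in order for the patient to continue to the SU phase of the study and be randomized"; the first condition is reaching the MCRT of 300 mg without symptoms. The protocol's Study Design section agrees: "Subjects who are able to consume more than 300 mg of peanut protein will be randomized to an interval between 1 and 17 weeks". The protocol synopsis and Protocol 5.5 also limit randomisation to children who pass.

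**What the methods use.** For the threshold distribution, SAP 8.1.2 treats a child as "left censored if individual fails on the smallest dose administered", and SAP 10.1 says "then left-censoring occurred, and the NOAEL was set to zero with the LOAEL set as that first dose". For time to loss, SAP 4.3 (second item) and SAP 8.1.2 put children below the MCRT at time zero. The SAP 10.1 likelihood sets X = 0 "for those subjects who do not meet MCRT" and gives that event its own logistic covariate model. SAP 10.1 names no population for ED05/ED10.

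**The concern.** ED05/ED10 is the first primary endpoint and is stated for the peanut-allergic population. It is a lower-tail quantile. Section 7, read with SAP 4.3, excludes exactly the children in that tail, and excludes them because of the outcome being measured. An analyst working from section 10.1 keeps them; one working from sections 7 and 8.1 drops them. Two competent analysts could therefore report different primary results from the same plan.

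Two further analyses are affected:

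- **The X = 0 component.** Within ITT it would contain no gate failure. It could hold only withdrawals (SAP 8.1.3) or, if d in SAP 10.1 is a single dose, children with d = 200 mg, who have in fact taken 300 mg cumulatively and been randomised.
- **The immune comparison.** SAP 3.2.1 compares desensitised children with those who failed, but ITT contains no month-48 failures. SAP 3.1.2 words the same comparison in terms of clinical tolerance, so the failed group is also ambiguous.

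**Working it through.** **1. The plan's own figures.** The documents give no gate-failure rate and no expected ED05 or ED10. The only sample size, 50, comes from the superseded two-arm design. It reproduces: 90% versus 50%, 2:1, two-sided 0.05, 80% power, normal approximation without continuity correction gives 15 + 30 = 45, and 45/0.90 = 50. It does not bear on this point.

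**2. Which cells ITT can contain.** The month-48 steps are 100, 200, 500, 800, 1300 and 2100 mg (SAP 4.2), so the cumulative doses are 100, 300, 800, 1600, 2900 and 5000 mg. With a gate at 300 mg cumulative, the intervals 0–100 and 100–300 mg are empty in ITT by design. A non-parametric ED05 or ED10 then cannot fall below 300 mg (200 mg on the single-dose scale), whatever the data. If the gate is read as strictly more than 300 mg, the 300–800 mg interval could also be emptied.

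**3. Distribution-free effect.** Let F be the threshold distribution of all challenged children and p the share failing the gate. Above the gate, the randomised-only distribution is (F(x) − p)/(1 − p). Setting this equal to q gives F(x) = p + q(1 − p).

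| p failing | Reported ED05 is really | Reported ED10 is really |
|---|---|---|
| 3% | 0.03 + 0.05 × 0.97 = 7.9% | 0.03 + 0.10 × 0.97 = 12.7% |
| 10% | 0.10 + 0.05 × 0.90 = 14.5% | 0.10 + 0.10 × 0.90 = 19.0% |
| 16% | 0.16 + 0.05 × 0.84 = 20.2% | 0.16 + 0.10 × 0.84 = 24.4% |

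**4. In numbers of children.** Assume 46 are challenged (51 enrolled less 10%: 51 × 0.9 = 45.9). Since 0.05 × 46 = 2.3 and 0.10 × 46 = 4.6, three failures put the all-challenged non-parametric ED05 at or below the gate, and five do so for ED10. In ITT neither can happen.

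**5. Effect on a parametric fit.** Assumptions: log-normal thresholds on the cumulative scale, gate at 300 mg cumulative, failure share p, log-SD s, so that the log-mean is ln 300 − s·z(p), where z(p) is the standard normal p-quantile. An interval-censored log-normal model is fitted by maximum likelihood to the expected counts, with and without the two lowest intervals. Results for s = 1.2, with the ED05 ratio over s = 0.8 to 1.6:

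| p | ED05, all vs randomised (mg) | ED10, all vs randomised (mg) | ED05 ratio, s = 0.8 to 1.6 |
|---|---|---|---|
| 2% | 490 vs 611 | 758 vs 906 | 1.14 to 1.39 |
| 5% | 300 vs 450 | 464 vs 652 | 1.30 to 1.80 |
| 10% | 194 vs 366 | 300 vs 518 | 1.55 to 2.44 |
| 20% | 114 vs 312 | 177 vs 425 | 2.06 to 3.92 |

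Weibull fits to the same counts also move upward.

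**6. At the trial's size.** Simulated trials of 46 children (500 per scenario, s = 1.2, medians 3000, 1500 and 1000 mg, giving 2.8%, 9.0% and 15.8% failing) show the same pattern. The ratio of median ED05, randomised to all, is 1.3, 1.8 and 2.3 on the cumulative grid and 1.2, 1.6 and 2.0 on the single-dose grid of SAP 10.1.

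**7. Chance that the problem does not arise.** With 45 children the probability of no gate failure is 0.98^45 = 40% at a 2% rate, 0.95^45 = 10% at 5%, and 0.90^45 = 0.9% at 10%.

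**The case against.** **The intended handling can be inferred.** SAP 4.3 (second item), 8.1.2 and 10.1 all give the gate failures an explicit place, so an analyst carrying out section 10.1 would keep them. This is a fair account of the likely intent. But sections 7 and 8.1 are the places that name a population, and they name the set without these children.

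**Perhaps everyone challenged is randomised.** SAP section 4 says "At the same visit, subjects are randomized to one of the 17 weeks of SU phase" without repeating the gate, Protocol 5.9 places assignment at the month-48 challenge, and SAP 4.4 reveals the week only afterwards. Section 7 also speaks of randomisation for assessing desensitisation as well as SU. On that reading, failures are assigned a week but skip the final challenge, and the sections agree. However, these passages concern when the week is assigned or revealed. They do not remove the explicit condition in SAP 4.3 or the matching protocol text. If this reading was meant, those passages need correcting.

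**The bias may be small.** Protocol 5.2 expects about 45 children eligible for randomisation after 10% dropout. From 50 enrolled (50 × 0.9 = 45) that leaves no gate failures, from 51 about one, and from 55 (49.5) about 4.5, or 9%. This stands as a caution: failure shares well above 9% go beyond what that section implies, and the sizes in mg rest on assumed spreads. It does not change the direction of the bias or the contradiction.

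**Conclusion.** The concern holds. Sections 7 and 8.1 of the SAP cannot be applied together with 8.1.2 and 10.1, and following section 7 conditions the first primary endpoint on its own outcome. The direction is certain if any child fails the gate: both doses are overstated. The quantile shift needs no distributional assumption. The sizes in mg are illustrative, because they rest on an assumed failure share, log-normal thresholds, the assumed log-SD and a gate at 300 mg cumulative. With no failures there is no bias. The point must be fixed before analysis because the choice of population can change the reported primary result.

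**What to change.** In SAP section 7, add a month-48 challenge population and replace the sentence that assigns all efficacy analyses to ITT. Suggested text:

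> *Month-48 Challenge Population: every child who undergoes the month-48 DBPCFC, whether or not later randomised, excluding the crossover participant whom Protocol 5.2 leaves out of the analysis. It is used for ED05/ED10, the NOAEL/LOAEL tables, covariate effects on the threshold, the X = 0 component of the time-to-loss likelihood, and the immune comparison of desensitised children with those who failed. The randomised population is used for time to loss after SLIT is stopped, given X > 0.*

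Align SAP 8.1, 10.1 and 10.2 and Protocol 8.1.2 with this. Four details should be settled in the same edit:

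- **Withdrawals before month 48.** They have no month-48 interval. Leave them out of the ED05/ED10 fit, report their number, and keep them separate from gate failures in the X = 0 component. Add a sensitivity analysis that counts them as failures and states the dose interval used, for example 0 to 300 mg cumulative.
- **Dose scale.** State whether d and the MCRT are cumulative or single doses.
- **The failed group.** Define it once for SAP 3.1.2 and 3.2.1.
- **Gate wording.** The protocol synopsis, Study Design, Protocol 5.5 and SAP 4.3 word the 300 mg condition differently, so a child at exactly 300 mg is in or out depending on the passage. These passages must be reconciled.

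The cost is wording only. No extra data are needed, and SAP section 1 records 24 children still waiting for the month-48 challenge when it was written. The price is lower reported ED05 and ED10 if any child fails the gate.
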